9.4. Sample size and Power calculation

The safety, reactogenicity, and tolerability of the vaccine regimens are the primary endpoints for this study. The table below demonstrates effect size with a power of 80%, calculated at a variety of sample sizes.

In [Table 11](#), the sample size calculation for the antibody titer (secondary outcome) will be based on the published data from Pitisuttithum P et.al¹⁸. For the analysis of this experiment we plan on observing a single measurement of peak antibody level per participant. Thus, the study is designed around a 1-way ANOVA model. Tukey's method will be used in the pairwise comparison test. In the analysis we looked at the size of the error bars on the peak of the log antibody titer and based upon our visual inspection we assumed that the residual standard deviation is = 0.2. A sample size of approximately 20 participants per arm was selected to provide $\geq 80\%$ power to detect the effect size of ≥ 0.202 between study arms. Statistical significance will be set at $p=0.05$.

[Table 12](#) depicts SAE or AESI rates and associated 95% confidence intervals in each potential grouping of interest given 0-5 participants with observed events. If we were to observe zero events within a single active study group ($n=20$), the upper limit of a 2-sided exact 95% CI would be 13.9% and true events above this could be ruled out at the $\alpha=0.025$ level.

Table 11: Sample size per arm and minimum effect size with 80% power, assuming residual standard deviation of 0.2

Part A: 3 Active Arms		
n per arm	Minimum effect size	Power
5	0.448	0.801
6	0.398	0.801
7	0.362	0.801
8	0.334	0.800
9	0.312	0.800
10	0.294	0.801
11	0.280	0.804
12	0.266	0.802
13	0.254	0.800
14	0.244	0.800
15	0.236	0.803
16	0.228	0.804
17	0.220	0.801
18	0.214	0.803
19	0.208	0.803

Part A: 3 Active Arms		
20	0.202	0.802
21	0.198	0.806
22	0.192	0.801
23	0.188	0.803
24	0.184	0.804
25	0.180	0.803
26	0.176	0.802
27	0.174	0.808

Table 12: Exact 95% Clopper-Pearson CI for the SAE Rate in Each Study Group

Number of Participants with Event	All Active Groups (n=60)	Any Active Group (n=20)	Arm 1 (n=22)	Arms 2 or 3 (n=19)
0	(0%, 4.9%)	(0%, 13.9%)	(0%, 12.7%)	(0%, 14.6%)
1	(<0.1%, 8.9%)	(0.1%, 24.9%)	(0.1%, 22.8%)	(0.1%, 26.0%)
2	(0.4%, 11.5%)	(1.2%, 31.7%)	(1.1%, 29.2%)	(1.3%, 33.1%)
3	(1.0%, 13.9%)	(3.2%, 37.9%)	(2.9%, 34.9%)	(3.3%, 39.6%)
4	(1.8%, 16.2%)	(5.7%, 43.7%)	(5.2%, 40.3%)	(6.0%, 45.5%)
5	(2.8%, 18.4%)	(8.7%, 49.1%)	(7.8%, 45.4%)	(9.1%, 51.2%)

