### 3.2.3. Exploratory endpoints

- Characterize plasma IgG and Immunoglobulin A (IgA) binding antibodies to HIV gp120, neutralizing antibodies, and non-neutralizing effector functions such as Antibody-Dependent Cell-Mediated Cytotoxicity (ADCC) and Antibody-Dependent Cell-Mediated Phagocytosis (ADCP) with emphasis on RV144 immune correlates of risk of HIV acquisition.
- Characterize B-cell functional specificities for each vaccination regimen by quantifying antigen-specific responses through B-cell Enzyme-Linked Immunosorbent Assay (ELISPOT), phenotyping the magnitude and activation status of B cell subsets via flow cytometry and isolation of monoclonal antibodies from selected vaccine recipients.
- Characterize innate immunity through quantification of soluble chemokines and cytokines and assessing the phenotype and function of cellular innate immune subsets such as Natural Killer Cell (NK), NKT, and dendritic cells.
- Characterize effects of host genetic polymorphisms on immune responses and characterize differentially expressed genes.

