## 4.2. Discussion of Study Design

This study design is a randomized, double-blind study, with three study arms of equal allocation (1:1:1) to assess the safety, tolerability, and immunogenicity of ranging doses of candidate vaccine A244/B.63521 with ALFQ adjuvant.

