## **5.7. Multiple Comparisons/Multiplicity**

All hypothesis tests will be performed as two-sided at the 5%-level, including planned immunogenicity analysis. Due to the limited sample size and the early phase of the study, adjustment for multiplicity across endpoints will not occur. For individual endpoints that involve a multitude of hypothesis testing (e.g., gene expression), the analysis will be adjusted for multiplicity using the Bonferroni-Holm step-down procedure [3]. Results will be considered on the strength of evidence. P-values  $\leq 0.05$  will be considered statistically significant evidence of a difference or association.

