## 8. IMMUNOGENICITY EVALUATION

### 8.1. Primary Immunogenicity Analyses

All summaries and analysis of immunogenicity data will be presented for the Immunogenicity Population. Humoral and cellular immunogenicity will be assessed primarily through descriptive statistics. Primary immunogenicity endpoints are IgG binding antibodies to g120 and antigen-specific CD4 and CD8 T cell responses.

The magnitude of plasma IgG (antigen-specific) responses will be measured by the endpoint titer at study weeks 0, 2, 4, 6, 8, 10, 24 and 48. Means or Geometric mean titers (GMTs) will be calculated for each group as appropriate based on the distribution, at each visit, and the per-participant peak response across all visits. Additionally, 95% confidence intervals (CI) will be computed using bootstrapping, or alternative methods. Results will be presented as exponentiated GMT and 95% CI. The distributions of GMTs will be compared across all vaccination groups via ANOVA (null hypothesis that the medians across all groups do not differ) at the 5%-statistical significance level, or using the Kruskal-Wallis test if ANOVA assumptions are violated; in the event Kruskal-Wallis testing is implemented the shape and scale uniformity across groups will be assessed for validity and results interpretation. Pairwise comparisons of GMT responses between dose groups at follow-up time points will be evaluated using a two-sided Mann-Whitney U test, with a Bonferroni-Holm step-down for adjusting p-values for multiple comparisons. Where necessary and appropriate, False Discovery Rates (FDR) will be calculated and reported using the Benjamini-Hochberg (BH) method.

The number and percentage of positive IgG responses to binding targets will be presented by vaccination group and visit based on input from the laboratory team. Differences between vaccinations groups will be evaluated using Fisher's exact test, or chi-squared tests.

Durability of IgG response will be assessed for each participant by estimating the decline in  $\log_{10}$  IgG from peak to 6 and 12 months (weeks 24 and 48 respectively) post final vaccination.

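### SAP 5.7 fixes Bonferroni-Holm for the exploratory gene-expression endpoint; Benjamini-Hochberg at a stated 5% FDR fits a discovery aim better, and SAP 5.7, 8.1, 8.2 and 11.1 should be aligned on it

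*SAP*

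**What the plan says.** SAP 5.7 sets the general level: "All hypothesis tests will be performed as two-sided at the 5%-level, including planned immunogenicity analysis". It then says that "adjustment for multiplicity across endpoints will not occur", because the sample is small and the phase early. For one endpoint that involves many tests it requires Holm, with gene expression as its example: "e.g., gene expression), the analysis will be adjusted for multiplicity using the Bonferroni-Holm step-down procedure".

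The endpoint concerned is listed in SAP 3.2.3 as exploratory: "Characterize effects of host genetic polymorphisms on immune responses and characterize differentially expressed genes". The platforms are DNA microarray and RNA sequencing (SAP Table S1; Protocol 8.3.5).

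Three other places bear on the rule:
- SAP 8.1, in the paragraph on IgG titers, adds that, where necessary and appropriate, "False Discovery Rates (FDR) will be calculated and reported using the Benjamini-Hochberg (BH) method".
- SAP 8.2, which governs the exploratory assays, says they otherwise follow a process similar to 8.1. For significance and multiplicity it refers to Section 5.8; the SAP contents end that chapter at 5.7.
- SAP 11.1 mentions FDR, as appropriate, for the week-10 interim analysis.

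Protocol 9.6.3 asks only that further exploratory comparisons be adjusted as appropriate.

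**The concern.** Holm limits the chance of even one false positive in the whole family. That protects a confirmatory claim. It is a costly standard for a screen whose product is a list of candidate genes for follow-up, because the first threshold is 0.05 divided by the number of tests. The SAP waives adjustment across endpoints on grounds of sample size and phase, and in the next sentence applies its strictest correction to the assay likely to have the most tests.

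At stake is the reading of the transcriptomic result. The trial exists to compare ALFQ doses, and a nearly empty gene list could be taken to mean that dose does not alter expression. In addition, a fixed Holm rule beside discretionary FDR elsewhere leaves room to choose the method after results are seen.

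**Working it through.** **Inputs from the documents.** Two-sided 5% level (SAP 5.7). Arm size: "A sample size of approximately 20 participants per arm was selected" (Protocol 9.4), with equal allocation (SAP 4.2). For log peak titer, "we assumed that the residual standard deviation is = 0.2", with a minimum effect of 0.202 (Protocol 9.4), so 0.202/0.2 = 1.01 SD. This is a titer figure, borrowed only as a benchmark for what the trial is sized to see.

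**Assumed, because the documents are silent.** Number of genes m from 1,000 to 20,000; true effect per affected gene from 0.8 to 2.0 SD; share of genes affected from 1% to 10%; independent genes; one pairwise contrast at one visit.

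**Step 1: the plan's own figure.** One-way ANOVA, means 0, 0.101 and 0.202. The noncentrality is 20 × (0.101² + 0 + 0.101²)/0.2² = 10.20. With 2 and 57 df the power is 0.8017, against 0.802 in Protocol Table 11. Rows n = 5, 10, 15 and 27 also reproduce (0.8014, 0.8006, 0.8035, 0.8084).

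**Step 2: Holm's first step.** Two-sample t-test, 38 df, level 0.05/m, noncentrality d × √(20/2); for d = 1.01 this is 3.19.

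| m | 0.05/m | critical t | 1.01 SD | 1.5 SD | 2.0 SD |
|---|---|---|---|---|---|
| 1 | 0.05 | 2.02 | 87.5% | 99.6% | 100% |
| 1,000 | 0.00005 | 4.57 | 11.6% | 57% | 94% |
| 5,000 | 0.00001 | 5.09 | 5.3% | 39% | 86% |
| 10,000 | 0.000005 | 5.31 | 3.7% | 33% | 81% |
| 20,000 | 0.0000025 | 5.53 | 2.5% | 26% | 76% |

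Later Holm steps use 0.05/(m − r) after r rejections. With 5% of genes affected this loosens the threshold by a factor of about 1/0.95 at most, so the first step is close to the whole procedure. A three-arm F test at 1.01 SD falls from 80.2% unadjusted to 8.3%, 3.8%, 2.6% and 1.8% for the same four gene counts. For 80% power, Holm needs an effect of 1.74 SD (1,000 genes) to 2.05 SD (20,000 genes).

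**Step 3: BH at 5%.** With many genes and a share π affected, the BH cut-off t solves t = 0.05 × [(1 − π)t + π × power(t)].
- 1.01 SD, π = 5%: t = 0.00097, power 0.370. Check: 0.05 × (0.95 × 0.00097 + 0.05 × 0.370) = 0.00097.
- 1.01 SD, π = 1%: t = 0.000071, power 0.136. Check: 0.05 × (0.99 × 0.000071 + 0.01 × 0.136) = 0.000072, equal within rounding.

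Simulation over 1,000, 10,000 and 20,000 genes gave these shares of true effects found:

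| effect | share affected | Holm | BH |
|---|---|---|---|
| 0.8 SD | 1% | 0.6–2.5% | 2–4% |
| 0.8 SD | 5% | 0.6–4% | 8–12% |
| 1.01 SD | 1% | 3–9% | 15% |
| 1.01 SD | 5% | 3–12% | 37–39% |
| 1.01 SD | 10% | 2.5–11% | 48–50% |
| 1.5 SD | 1% | 26–59% | 79–81% |
| 1.5 SD | 5% | 26–58% | 92% |
| 2.0 SD | 1% | 75–94% | 98–99% |
| 2.0 SD | 5% | 76–94% | 99.7–99.8% |

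At exactly 1.0 SD with 15,000 genes, BH finds about 35% (5% affected) or 12% (1% affected). The simulated false discovery proportion under BH ran from about 2% to 6.5%; in expectation it is 0.05 × (1 − π), so 4.5% to 4.95%.

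**The case against.** Holm is valid, and the endpoint is exploratory, may be reported separately (SAP 5.2), and drives no primary, secondary or safety conclusion. That stands, and it limits how much weight the point carries.

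Two stronger readings are tempting, and the documents do not support them.
- A reader might infer that Holm would miss nearly every true dose effect. That holds near 1 SD with thousands of genes. At 2 SD Holm finds most effects, and neither the gene count nor the effect size is stated in the plan.
- A reader might infer that the SAP reserves BH for titers. It does not: 8.1 words it permissively, 8.2 says exploratory assays follow a similar process, and 11.1 mentions FDR again. Still, none of these replaces the specific rule in 5.7, and the one cross-reference that should settle the matter leads nowhere.

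It is also fair that the calculation covers one contrast. SAP 8.2 allows paired changes from baseline, and Protocol 8.3.5 speaks of expression that correlates with immunogenicity; neither was examined. Correlated genes were not simulated, and they would make the realised false discovery proportion more variable. Pooling several contrasts or visits into one family would lower Holm's power further.

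Finally, BH is only a partial cure. With 1,000 genes, 1% affected and an effect of 1.01 SD, the gain is from about 9% to 15%.

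**Conclusion.** The concern holds in a conditional form. SAP 5.7 assigns family-wise control to a discovery endpoint, and four sections of the SAP are not reconciled on the method. BH found more true effects than Holm in every setting tried. The gain is largest at 1 to 1.5 SD when at least a few per cent of genes are affected, and small when very few genes are affected or effects are below 1 SD. These sizes rest on the assumed gene count, effect size and share affected, on independence, and on a 20 v 20 t-test.

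This is an inexpensive improvement to an exploratory analysis. It does not show that the planned analysis is invalid.

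**What to change.** In SAP 5.7, for gene expression (microarray and RNA sequencing) and other high-dimensional exploratory assays, replace Holm with Benjamini-Hochberg at a stated 5% FDR. Apply it across all genes within each pre-stated contrast and visit, including gene-level pairwise dose contrasts, and list those contrasts and visits. Antibody profiling belongs here too: Protocol 8.3.3 expects 900 to 1,000 data points per sample, a scale at which Holm's first step already leaves about 12% power at 1.01 SD if each is tested.

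Keep Holm for the three pairwise dose comparisons of the IgG titer and T-cell endpoints in SAP 8.1. Align 8.1 and 11.1 with this division, and correct the Section 5.8 reference in 8.2. The Holm citation [3] in 5.7 also needs an entry, since the reference list has two.

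The cost is a few sentences. Protocol 9.6.3 leaves the adjustment open, so the change does not conflict with it, and SAP 11 provides for updating before unblinding. The report should state two limits: about 5% of the genes listed within each contrast and visit are expected to be false discoveries, and a short list is not evidence that dose has no effect.

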## 6. STUDY PARTICIPANTS

### 6.1. Disposition of Participants

The number of participants who enroll in the trial, and the number and percentage of participants who complete each assessment, will be presented by vaccination group. A flowchart showing the disposition of study participants, adapted from the Consort Statement, will be included, including the number of participants enrolled, withdrawn, lost to follow-up, and analysed by treatment group. The percentage of participants who withdraw from the trial or discontinue the study drug, and reasons for withdrawal or discontinuation, will be summarized by group and given in a listing.

### 6.2. Demographic and Other Baseline Characteristics

Participant demographics and baseline characteristics, listed in section 4.9, will be summarized by vaccination group, using the statistics described in Section 5.1.

### 6.3. Prior and Concurrent Medical Conditions

Prior and concurrent medical conditions, collected as part of medical history assessments, will be summarized by vaccination group. Any medical conditions reported subsequent to enrollment that meets study exclusion criteria will be presented in a listing.

### 6.4. Prior and Concomitant Medications

Any concomitant medications reported subsequent to enrollment that meet study exclusion criteria will be presented in a listing.

### 6.5. Measurements of Study Product Compliance

A listing presenting each participant's vaccination group and product received will be presented. Any participants who receive the wrong study vaccination and those who are randomized but not vaccinated will also be presented in a line listing.

### 6.6. Protocol Deviations

All major protocol deviations will be summarized by vaccination group and presented in a listing. A summary of protocol deviations by vaccination group will also be presented in a table.

## 7. SAFETY EVALUATION

All summaries and analyses of safety data will be presented for the Safety Population. Safety summaries for the occurrence and severity of SAEs, AEs, AESIs, and unsolicited AES will be presented by vaccination group. The denominator for the percentages may be based on the number of non-missing observations for an assessment or based on the number of participants in a population. This will be described for each exhibit.

### 7.1.1. Solicited Reactogenicity Events

The occurrence of local and systemic reactogenicity symptoms will be listed and summarized for each vaccination group as the proportions of patients experiencing safety events along with 95% exact Clopper-Pearson CI for the underlying probability of the event. These will be described overall. Differences in the proportion of patients with safety outcomes in each group will be assessed using either the Fisher exact test, or Pearson chi-square test, as appropriate.

The likelihood of reporting solicited local and systemic AEs will be compared across groups via exact binomial tests. If computational challenges arise, Chi-squared tests may be used instead.

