Participants will be followed for a total of 12 months post final vaccination. Serious Adverse Events and SAEs will be recorded at all visits along with timing and possible attribution to Investigational Product. Because this clinical trial involves an adjuvant, Adverse Events of Special Interest AESIs and Medically Attended Adverse Events (MAAE) will also be assessed. Safety laboratory analyses of complete blood count, liver function tests, urinalysis, and pregnancy test in females will also be performed. Safety results will then be compared among dose arms.

Statistical Methods:

RV 575 is designed to optimize ALFQ dosing. The primary objective is to compare dose- dependent safety and reactogenicity of ALFQ. For safety analyses, the occurrence of local and systemic reactogenicity symptoms, AEs, and SAEs will be assessed as the proportions of participants experiencing such safety events and compared among the three study arms. The secondary objective is to assess immunogenicity.

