**DATE: 22 January 2024**

**SAP Revision History**

Revision Date	Analyst	Revisions/Justification
01Feb2023	[name]/[name]	Additional sensitivity analyses due to unanticipated vaccinations occurring out of study window
21 December 2023	[name]/[name]	Detailing interim Analysis plans for Humoral Immunity and dose response
11 January 2024	[name]/[name]	Finalized edits and Added CONSORT example diagram
18 January 2024	[name]/[name]	Clarified Interim analysis specifications for cellular response

Trial Initiation Date: first participant screened 08 Sept 2022

Trial Completion Date: last participant visit 29 Oct 2024

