## 2. INTRODUCTION

The purpose of this study is to optimize ALFQ dosing. This study is a Phase 1 three-arm randomized double-blind clinical trial. The primary outcomes for this study include safety assessments and secondary outcomes include cellular and humoral immune responses. Safety will be assessed through the frequency of the overall and specific post-vaccination reactions. Blood will be collected to assess humoral, cell-mediated, and innate immune responses.

Healthy adults not living with HIV, who are available for 12 months will be enrolled. A total of 60 participants will be enrolled in one of three arms, each comprised of 20 candidate vaccine recipients in an overall allocation of 1:1:1. A sentinel group will consist of the first 6 participants enrolled and will be used to assess safety prior to enrolling the remaining 54 participants. Each study arm will receive identical doses of A244 and B.63521 (300 micrograms of each protein). In addition, arm 1 will receive 200 micrograms of ALFQ. arm 2 will receive 100 micrograms of ALFQ; and arm 3 will receive 50 micrograms of ALFQ. The safety, reactogenicity, and immunogenicity will then be compared among the three arms to determine the optimal dose of ALFQ.

All vaccinations will be split into 2 half doses, which will be administered intramuscularly (IM) into the same deltoid muscle. Vaccinations will occur at months 0, 1, and 2. The second vaccination will be administered into the contralateral deltoid at study month 1 compared to the first vaccination at study month 0. The third vaccination at study month 2 will be administered into the same deltoid as the first vaccination at study month 0. Participants will be followed for 12 months following the last study vaccination.

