## 4. INVESTIGATIONAL PLAN

### 4.1. Overall Study Design and Plan

This is a phase I randomized, double-blind clinical trial to optimize ALFQ dosing among healthy adults not living with HIV. A total of 60 participants will be enrolled to one of three arms (N=20 in each arm) with each arm receiving 300 micrograms of A244 and B.63521. In addition, arm 1 will receive 200 micrograms of ALFQ, arm 2 will receive 100 micrograms of ALFQ, and arm 3 will receive 50 micrograms of ALFQ. The safety, reactogenicity, and immunogenicity will then be compared among the three arms to determine the optimal dose of ALFQ.

All vaccinations will be split into 2 half doses which will both be administered intramuscularly (IM) into the same deltoid muscle. Vaccinations will occur at months 0, 1, and 2. The second vaccination will be administered into the contralateral deltoid at study month 1 compared to the first vaccination at study month 0. The third vaccination at study month 2 will be administered into the same deltoid as the first vaccination at study month 0. Participants will be followed for 12 months following the last study vaccination. Table S2 provides a schematic for the study design.

**Table S2:** Study Design

Number of participants (N) = 60		Vaccination schedule in months (days)		
	Number of participants (N)	Month 0 (Day 1)	Month 1 (Day 29)	Month 2 (Day 57)
Arm 1	20	300µg A244	300µg A244	300µg A244
		300µg B.63521	300µg B.63521	300µg B.63521
		200µg ALFQ	200µg ALFQ	200µg ALFQ
Arm 2	20	300µg A244	300µg A244	300µg A244
		300µg B.63521	300µg B.63521	300µg B.63521
		100µg ALFQ	100µg ALFQ	100 µg ALFQ
Arm 3	20	300µg A244	300µg A244	300µg A244
		300µg B.63521	300µg B.63521	300µg B.63521
		50µg ALFQ	50µg ALFQ	50µg ALFQ

The schedule of events is given in Table S3 below, for reference

Table S3: Schedule of Events (SOE)

Visit Number	0	1	2	3	4	5	6	7	8	9	10  /Exit 4	Phone Follow-up #1	Phone Follow-up #2
Visit Type	Screen	V1	Safety & Immun	V2	Safety & Immun	V3	Safety & Immun	MAAE follow-up	MAAE follow-up				
Visit Day	-30 to -3	1	15	29	43	57	58-59	64	71	169	337	365	393
Window			± 3d	± 7d	± 3d	± 7d	± 3d	± 3d	± 3d	± 7d	± 7d	± 7d	± 7d
Visit Week	0	2	4	6	8	8	9	9	10	24	48	52	56
Clinical													
Briefing and Contact Information	X												
Informed Consent	X												
Test of Understanding	X												
Enrollment and Randomization	X												
Vaccination	X			X		X							
Vital Signs and Physical Exam 	X	X	X	X	X	X	X	X	X	X	X	X	X

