## 5. GENERAL STATISTICAL CONSIDERATIONS

### 5.1. General Principles

All continuous variables, with appropriate transformations (e.g., log, square root, or arcsin) applied as necessary, will be summarized using the following descriptive statistics: n (non-missing sample size), mean, standard deviation, median, minimum, and maximum. The frequency and percentages (with the non-missing sample size as the denominator) of observed levels will be reported for all categorical measures. Exact Clopper-Pearson confidence intervals will be computed for binary variables, where applicable. For continuous variables, confidence intervals will be computed based on the t-distribution with  $n-1$  degrees of freedom, where  $n$  denotes the number of observations. If the data are found to be non-normal, and the sample size is insufficient for application of the central limit theorem (which states that in sufficiently large samples, the sample mean is approximately normal), non-parametric bootstrapped confidence intervals may be calculated instead.

In general, all data listings will be sorted by treatment group and participant, and when appropriate by visit number within participant. All summary tables will be structured with a column for each treatment group in the order presented in the protocol and will be annotated with the total population size relevant to that table/treatment group, including any missing observations.

For hypothesis tests of continuous endpoints, an ANOVA will be preferred for global tests and t-tests will be preferred for pairwise tests. If histograms of the analysis data do not appear by visual inspection to be approximately normal, even after appropriate transformations, or if the sample sizes for comparisons groups are too small for the application of the central limit theorem, a Kruskal-Wallis test will be utilized instead of an ANOVA, and a Wilcoxon rank-sum test will be utilized instead of a t-test. For tests of categorical endpoints, a chi-square test or, if cell counts prohibit the use of a chi-square test, a Barnard's test or Fisher's exact test will be used as appropriate.

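### No planned between-arm test uses the order of the three ALFQ doses or estimates a dose effect; a pre-specified trend analysis should be added beside the planned tests

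*SAP*

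**What the plan says.** **Aim and design.** The Statistical Methods part of the protocol synopsis states: "The primary objective is to compare dose- dependent safety and reactogenicity of ALFQ". SAP 4.1 gives arm 1 200 µg and continues: "arm 2 will receive 100 micrograms of ALFQ, and arm 3 will receive 50 micrograms of ALFQ". SAP 2 describes the arms as "each comprised of 20 candidate vaccine recipients in an overall allocation of 1:1:1". The doses form a doubling series, so they are equally spaced on the log2 scale.

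**Safety tests.** In SAP 7.1.1, differences in the proportion with solicited events "will be assessed using either the Fisher exact test, or Pearson chi-square test". The same section adds that the likelihood of reporting such events "will be compared across groups via exact binomial tests". Protocol 9.6.2 plans pairwise comparisons that may be run at a two-sided 5% level, by the normal approximation or by another test such as Fisher's. SAP Table 7 has one p-value column for the three arms.

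**Immunogenicity tests.** For continuous endpoints SAP 5.1 states that "an ANOVA will be preferred for global tests and t-tests will be preferred for pairwise tests", with rank tests as the fallback. SAP 8.1 follows this for titers (ANOVA or Kruskal-Wallis, then Holm-adjusted Mann-Whitney tests) and uses Kruskal-Wallis and Mann-Whitney tests for T-cell responses. The interim humoral model in SAP 5.6.1 enters dose as a group; only time is said to be continuous. The interim AUC comparison there is an ANOVA.

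**Level.** SAP 5.7: "All hypothesis tests will be performed as two-sided at the 5%-level, including planned immunogenicity analysis".

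Neither document describes a trend test, an ordered contrast or a slope on dose.

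**The concern.** Each planned global test gives the same p-value if the labels 50, 100 and 200 are shuffled among the arms. Such a test asks whether the arms differ somehow. It does not ask whether reactions or titers rise with dose, which is what a dose-dependence aim is about. With two degrees of freedom and 20 per arm, it also spreads its power over patterns that nobody expects.

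The second gap matters at least as much. The plan yields a proportion with an exact interval for each arm, but no single number for the change per doubling of ALFQ, with its confidence interval. A team choosing a dose would have three wide intervals and a non-specific p-value. A moderate gradient could then be reported simply as no significant difference.

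**Working it through.** **1. Reproduce the plan's own figure.** Protocol Table 11 gives power 0.802 for n = 20 per arm, effect size 0.202 and SD 0.2, for a one-way ANOVA. Put the middle arm at the midpoint: means 0, 0.101, 0.202.

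- Noncentrality: λ = n·Σ(mᵢ − m̄)²/σ² = 20 × (0.101² + 0 + 0.101²)/0.2² = 20 × 0.020402/0.04 = 10.201.
- Critical value F(2, 57) at 5% = 3.159.
- Power = 0.8017, against 0.802 stated. The rows for n = 5, 10, 15 and 27 also match.

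The tabulated power therefore corresponds to an evenly graded effect.

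**2. Use the dose order on that same effect.** Linear contrast in log2 dose, weights (−1, 0, 1):

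- Noncentrality = 0.202/(0.2 × √(2/20)) = 0.202/0.06325 = 3.194, with 57 df.
- Critical t = 2.002; power = 0.881.

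The gain is 88.1 − 80.2 = 7.9 points. The ANOVA needs 24 to 25 per arm to match it (87.5% at 24, 88.9% at 25). For comparison, the 50-versus-200 pair alone has 78.2% by Tukey's method and 87.5% by an unadjusted two-sample t-test.

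**3. Solicited events.** The documents give no rates by arm, so the rates below are assumptions. Method: enumerate all 21 × 21 × 21 outcomes for three arms of 20 and sum binomial probabilities over the rejection region at two-sided 5%. With scores 0, 1, 2 (log2 dose) and equal n, the trend statistic is

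z² = (x₂₀₀ − x₅₀)² / [40·p̄(1 − p̄)],

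with p̄ pooled over all three arms. Power in percent:

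| Assumed rates 50/100/200 µg | Fisher 3×2 | Exact trend | Chi-square, 2 df | Asymptotic trend | 50 vs 200, normal approx. | 50 vs 200, Fisher |
|---|---|---|---|---|---|---|
| 30/45/65% | 48.7 | 57.5 | 50.9 | 58.4 | 58.9 | 46.8 |
| 30/50/70% | 61.2 | 70.3 | 63.3 | 70.8 | 71.3 | 59.9 |
| 10/25/45% | 57.1 | 67.6 | 63.4 | 74.4 | 74.2 | 62.4 |
| 30/70/70% (plateau) | 74.9 | 70.4 | 77.3 | 72.1 | 71.3 | 59.9 |
| 30/30/70% (step) | 74.9 | 70.4 | 77.3 | 72.1 | 71.3 | 59.9 |
| 20/60/30% (non-monotone) | 66.2 | 5.0 | 69.9 | 7.3 | 11.4 | 6.2 |

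The pairwise columns are unadjusted, at 5%. With all rates at 30%, the rejection rate is 3.8% for Fisher 3×2 and 3.3% for the exact trend test, so the exact test's gain is not bought with type I error.

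Over a wider set of graded shapes, the gain was 4 to 11 points (Fisher to exact trend) and 3 to 15 points (chi-square to asymptotic trend).

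**4. Why one pairwise test keeps up.** For 50 versus 200 by the normal approximation, z² = (x₂₀₀ − x₅₀)² / [40·p̂(1 − p̂)], where p̂ pools only those two arms. The numerator is the same as for the trend test, so the two nearly coincide.

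**The case against.** **The study is exploratory.** Protocol 9 says that it will characterise safety and immune responses descriptively, and the synopsis calls it exploratory. Each arm's proportion gets an exact interval, so a gradient would be visible. This stands as a limit on how much lost power matters. It does not remove the gap: the SAP still sets tests at 5%, Table 7 prints p-values, and a descriptive study is where an effect estimate is most useful.

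**A planned comparison already does as well.** The unadjusted 50-versus-200 test by the normal approximation (Protocol 9.6.2) has practically the power of the trend test, and the unadjusted t-test for titers comes within a point of the contrast. This stands. The power gain is real against the global tests, and for titers against Tukey. Setting the trend test against a 50-versus-200 test at a Bonferroni third of alpha would look worse for the plan, but no such split is planned for safety.

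**A trend test is not always better.** It loses about 5 points for a step or plateau, and nearly all power at 20/60/30%. A slope alone also does not say which dose suffices. This stands, and it rules out replacing the planned tests.

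**The protocol leaves room.** Protocol 9.6.2 allows an alternative procedure as appropriate. But a trend test chosen after unblinding would be post hoc.

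**The revision history.** A reader might infer from the log entry "Detailing interim Analysis plans for Humoral Immunity and dose response" that a promised analysis was left out. The documents do not support that. The entry is in a change log, concerns the interim humoral analysis, and can be read as describing the comparison of dose groups in SAP 5.6.1.

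**Conclusion.** The plan has no between-arm test that uses dose order and no estimate of the dose effect, although the synopsis words the aim as dose-dependent. That is a documentary fact and rests on no assumption.

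The size depends on the endpoint. For titers, on the plan's own Table 11 effect, ignoring order costs about 8 points against the one-way ANOVA (80% versus 88%); this assumes the evenly graded means that reproduce the table. For solicited events the cost rests on assumed rates: about 7.5 to 9 points at 30/50/70%, and roughly 3 to 15 over graded shapes. A reader might take a single figure of about 9 points as a property of the plan. It is not one, because neither document gives event rates and the figure varies with rates, comparator and shape.

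This is a cheap, worthwhile improvement, not a defect that invalidates the planned comparisons. Its firmer benefit is the estimate per doubling of dose; the power gain is conditional.

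**What to change.** **SAP 7.1.1 and Table 7.** Beside the planned unordered and pairwise tests, add a pre-specified exact Cochran-Armitage trend test with scores equal to log2 ALFQ dose, and the odds ratio per doubling of dose with its 95% CI. Name an estimation method that works when an arm has no events or all events, such as exact or Firth logistic regression.

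**SAP 8.1.** Add the linear contrast in log2 dose for log peak titer, with its slope and 95% CI.

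**Wording.** State that the trend results are reported alongside the unordered and pairwise results and replace neither, because a trend test can miss a plateau or a non-monotone pattern. Record the change in SAP 11 before unblinding. If the codes have already been broken, report the analysis and label it post hoc.

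**Cost.** A few sentences, a few lines of code, an extra column in Table 7, and one more reported test per endpoint in a plan that does not adjust across endpoints. No participant, visit or sample changes.
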